## 1. Background:

The human skin aging process is characterized by thinning dermis, atrophy of the extracellular matrix, and reduced collagen synthesis[1]. Loss of collagen in the dermis is of aesthetic concern, as it is the main structural support in the dermis and its loss results in skin laxity. Photo-damaged skin, mostly due to UVR, causes degradation of elastic fibers. This is histologically seen as disorganized tangles of elastin. Additionally, as we age, skin tends to appear more dry due to its poor hydration and turgor capacity[1]. The use of minimally invasive aesthetic treatments in reducing signs of aging has been gaining in popularity over surgical treatments in recent years[2]. Several energy types including, laser, radiofrequency, infrared, and ultrasound, have been developed for facial rejuvenation[3]. These treatments induce controlled thermal damage into the dermis and cause collagen contraction and neocollagenesis resulting in skin tightening over several months[2]. The effects of facial rejuvenation treatments on collagen have been well defined in literature, however, the role of elastin in facial rejuvenation has not been well studied.

In facial skin aging, the skin loses elasticity and begins to sag. Minimally invasive bipolar radiofrequency produces a controlled thermal injury in a fractional manner without damaging the dermal-epidermal junction, epidermis or subcutis[5]. Radiofrequency, unlike lasers, are chromophore-independent providing better penetration than lasers, and spare sweat glands, sebaceous glands, and hair follicles[5,6].

The Profound System is a bipolar fractional radiofrequency device which uses microneedles and thermal heat to stimulate neocollagenesis and neolastosis.

This study intends to evaluate the safety and effectiveness of the Profound System on submental tissue and its effect on skin tightening and lift, as an exploratory evaluation. This device has been FDA cleared and commercially available since 2016 for treatment of facial wrinkles and improvement in the appearance of cellulite. This device is well-studied and frequently used on facial skin.

There are alternative treatments that have demonstrated a decrease in laxity of the facial skin. We feel that the Profound System may be able to produce clinically significant improvement in laxity of the neck skin. This device has been used in the Department of Plastic Surgery clinic off-label for over three years for this purpose. Additionally, our research team conducted a study using Ulthera, an ultrasound device, approximately 10 years ago; the results of this study led to its FDA approval for the treatment of lax neck skin. Therefore, our experience with this device and with treating lax neck skin have guided our decision to conduct this study.

## 2. Purpose:

The purpose of this study is to evaluate the safety and efficacy of bipolar fractional radiofrequency treatment via use of the Profound System to achieve skin tightening and contour change in lax submental (beneath the chin) tissue.

Overall assessment of clinical outcome and safety will be based on clinic visits and measurements of volume difference and lift obtained by the Vectra H2 3D Imaging System and Stand-up Vectra (Canfield Scientific, Parsippany, NJ). Additionally, evaluation of pre- and post- procedural photos/video obtained via the 3D Imaging Systems will be performed comparing Baseline and 180 Days by blinded raters. These photos will be identifiable full-face photos, and subjects will be adequately informed of such. Two unblinded clinician's assessments of satisfaction will be characterized using the five-point Global Aesthetic Improvement Scale (GAIS) at the final follow up visit, one based on a live assessment and one based on photos. Subjects will also undergo high-resolution ultrasonography, optical coherence tomography, transepidermal water loss measurements, and/or BTC 2000 measurements for exploratory purposes. Additionally, consenting subjects will undergo two skin biopsies at the treatment site. Micro-biopsies using 0.33mm size punches will be used to extract core tissues before and after treatment for histological evaluation (tissue structure, elastin, collagen and hyaluronic acid expression) and gene expression assessment (elastin, other major extracellular matrix (ECM) molecules and elastin related genes).

From these exploratory procedures the improvement in laxity of the submentum can be evaluated in comparison to pre-treatment assessments.

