#### 10. Blinded Evaluation

Blinded evaluation will be performed by three physicians (dermatologist and/or plastic surgeons) to determine if the Profound System is effective for treatment to lift lax submental (beneath the chin) tissue.

Three qualified, non-treating clinicians will be trained to independently review Baseline and Follow-up photographs for each subject. The reviewers will be blinded to subject information and the temporal order of the photographs. No information will be provided to the reviewers that may allow them to determine the Baseline from the Follow-up imaging.

The pair of scans (labeled A and B) for each subject will include the pre-treatment photographs and post-treatment photographs (6 months follow-up).

The three blinded reviewers will individually be asked to review a randomized presentation of each subject's photographs. Each reviewer will be asked to record if he/she observes a difference between the pair (before and after) of the photographs. If the reviewer determines there is a difference, the reviewer will record which pair (A or B) he/she believes correlates to the Follow-up photographs. Improvement will be based on at least two of the three (2/3) blinded reviewers correctly identifying the post-treatment photographs. Secondarily, each reviewer will score the photo pairs in which they observed a difference for improvement via the GAIS.

Assessments of 2/3 blinded reviewers selecting "no change" will be considered as "no improvement, neither worsening". Assessments of 2/3 blinded reviewers selecting "change" and incorrect identification of the pre and post photographs will be considered as "worsened".

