The identified reviewers will be instructed that their participation is completely voluntary and has no impact on performance review at their institution. It will be clearly stated that consent is implied with the institution's survey completion. No identifying information about these blinded reviewers will be published but will be maintained in a secure manner to be monitored by the research team. If no incentive is to be provided to the blinded reviewers for their participation, this will be known to them prior to their participation. A waiver of documentation is requested as no subject Personal Health Information (PHI) will be collected, recorded, or shared. Blinded reviewers will be asked to attend one visit for the purposes of evaluating pre procedure photos and post procedure photos via a survey. Prior to the survey, study coordinator will ask for a verbal consent from the reviewers indicating approval to use their responses in the study. Reviewers will assess the images on a local computer.

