#### ***Photography***

The subject may be uncomfortable with sitting still for an extended period of time or from turning his/her body in various positions. Subjects may be sensitive to the bright and repeating flashes from the camera, which can sometimes cause headaches, irritation of the eyes, discomfort, after effects such as seeing spots, and in rare cases, could stimulate a migraine headache or epileptic seizure.

Photographs include a risk of identification, as these will be full face photos. Privacy will be protected to the greatest extent possible. Photos will only be identified by a unique subject identification number that contains no personal identifying information. All photos will be stored on a password secure drive, with only access by research personnel. For research purposes, photos may be used in scientific publications.

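### The blinded photo review uses identifiable full-face images and an unrestricted difference question, so visible changes outside the submental area can add false calls and, where they reveal order, inflate the improved count

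*Combined protocol and SAP*

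**What the plan says.** Section 2 (Purpose) has blinded raters compare Baseline and Day 180 photographs and video, and says of the photographs: "These photos will be identifiable full-face photos, and subjects will be adequately informed of such". Section 13, under Photography, repeats the point as a privacy risk: "Photographs include a risk of identification, as these will be full face photos".

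Section 10 (Blinded Evaluation) makes two promises about the same review: "The reviewers will be blinded to subject information and the temporal order of the photographs", and "No information will be provided to the reviewers that may allow them to determine the Baseline from the Follow-up imaging". The reviewers are independent of treatment: "Three qualified, non-treating clinicians will be trained to independently review Baseline and Follow-up photographs for each subject". The images are labelled A and B and presented in random order.

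The task itself is broad: "Each reviewer will be asked to record if he/she observes a difference between the pair (before and after) of the photographs". A reviewer who sees a difference then says which image is the follow-up. The scoring rule is: "Improvement will be based on at least two of the three (2/3) blinded reviewers correctly identifying the post-treatment photographs". Two of three reporting no change gives neither improvement nor worsening. Two of three reporting a change but picking the wrong image gives worsened. Pairs in which a reviewer saw a difference are also scored on the GAIS.

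Later in Section 10, a waiver of documentation for the reviewers is justified on the ground that "no subject Personal Health Information (PHI) will be collected, recorded, or shared".

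No section says that the images are cropped or masked for review, or that the questions are confined to the submental region.

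**The concern.** There are two separate problems.

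**Blind to subject information.** An identifiable face is information about the subject. Section 10 does not say what the term covers, and Section 2 describes the rated images in a way that conflicts with its plain reading. The statement that no PHI is shared has the same difficulty if reviewers are shown full-face images.

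**Blind to time order.** A/B labels and random presentation hide an image's position, not its content. The two images are about six months apart, and hair, make-up, tan and weight can all change in that time. The reviewer is asked about the pair as a whole, and a correct guess at order is scored as efficacy, so whatever reveals order counts as improvement whether or not the submental tissue changed. A cue that does not reveal order still does harm: it can turn a no-change vote into a change vote, which then falls on improved or worsened by chance.

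The study has no control group, and the clinicians' own GAIS ratings are unblinded (Section 2). The two blinded-review endpoints in Section 6.2 are the only efficacy ratings by observers that have protection from expectation.

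**Working it through.** The plan gives no error rate, power or expected proportion for the blinded review, so there is no figure to reproduce. The check is a reading of the text followed by an illustration.

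**Text.** Cues that the protocol itself acknowledges, and what it does about them in the images:

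- Hair: exclusion criterion x (Section 5.2) covers unwillingness to shave hair that could impair evaluation, but only in the treatment area.
- Make-up: cosmetics are removed before treatment (Section 7.3). No such step is listed before imaging in Sections 7.2 or 7.4.
- Tan: recent sun exposure is recorded at screening (Section 7.2), and Section 13 says sun avoidance or sunblock helps limit pigmentary change. If subjects act on that, skin tone could shift the same way in many pairs.
- Weight: listed at screening (Section 7.2) but not among the follow-up activities (Section 7.4).

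**Illustration.** Inputs from the plan: three reviewers, a two-of-three rule, up to 15 subjects. Assumed: no treatment effect; reviewers vote independently; each reports a difference with probability q; when a difference is reported, the follow-up image is picked correctly with probability p.

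A reviewer gives a correct pick with probability a = q × p. The probability that a subject is classed as improved is

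P = 3a²(1 − a) + a³.

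For q = 1 and p = 0.6, a = 0.6 and P = 3 × 0.36 × 0.4 + 0.216 = 0.648. For q = 0.5 and p = 0.6, a = 0.3 and P = 3 × 0.09 × 0.7 + 0.027 = 0.216.

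| q | p = 0.5 | p = 0.6 | p = 0.7 |
|---|---|---|---|
| 1.0 | 0.500 (7.5 of 15) | 0.648 (9.7) | 0.784 (11.8) |
| 0.8 | 0.352 (5.3) | 0.470 (7.1) | 0.590 (8.8) |
| 0.5 | 0.156 (2.3) | 0.216 (3.2) | 0.282 (4.2) |

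Reading across a row shows a cue that reveals order. Reading up the p = 0.5 column shows a cue that only makes reviewers report more differences: improved rises from 15.6% at q = 0.5 to 50% at q = 1, and worsened rises by the same amount, because guesses fall equally on both sides.

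A cue seen by all three reviewers would make their votes agree more often than independence allows. The table does not include this.

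**The case against.** The strongest case on the other side is that the plan is silent on an operational detail and does not contradict itself. The sentence in Section 2 is about privacy and consent, and full-face may describe capture only. Subject information may mean names, history and visit data; images carry only a subject number (Sections 13 and 16). Section 10 commits to giving reviewers nothing that reveals order, which would already cover dates and file metadata. Subjects also agree to avoid dermatological treatments and confounding aesthetic procedures (Sections 4 and 5.1 h), and the stated purpose of the review is submental lift.

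Much of this stands, and it limits the point. A reader might infer that the blind cannot hold, or that identifiable faces disclose which image came later. The documents do not support either. The reviewers are non-treating, a face reveals identity only to someone who knows the subject, and identity does not reveal order. Most of the cues are also non-directional: hair or make-up can differ either way and then add noise, including wrong picks. A tan reveals order only if it shifts the same way in most pairs and reviewers can tell which way; the documents give no enrolment calendar.

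What does not stand is the claim that labels and random order are enough. They do not act on image content, the difference question is not limited to the treated area, and abstaining from procedures does not control hair, make-up, tan or weight.

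**Conclusion.** The point holds as a weakness in the protection of the blind, not as a failed blind. The description of the rated images in Section 2 conflicts with the plain reading of Section 10's blind to subject information. The blind to order is not protected against visible changes outside the treated area.

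The size cannot be estimated from the documents. With no treatment effect, raising p from 0.5 to 0.7 adds 28 percentage points to the improved proportion if every reviewer reports a difference (78% against 50%), and 13 points if half do (28% against 16%, unrounded 28.2 and 15.6). The 50% starting value comes from the two-of-three rule with guessing, not from the use of full-face images; only the movement away from each row's starting value is due to order cues. All values of p and q are assumptions, as is independence between reviewers.

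The consequence is limited to secondary endpoints in an exploratory study of up to 15 subjects. The primary efficacy endpoint (Section 6.1.1) is measured by 3D imaging and does not depend on these ratings. This is a cheap improvement worth making before the images are reviewed.

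**What to change.** In Section 10:

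- Show reviewers only photographs and video cropped or masked to the submental, neck and jawline region, with the same pose, crop and colour/exposure settings for A and B.
- Limit the difference question, the choice of follow-up image and the GAIS score to that region.
- Have a reviewer who recognises a subject abstain for that pair, and state how a pair with fewer than three votes is classified.
- Define what subject information covers.

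In Section 2, state that full-face describes what is captured, not what blinded reviewers are shown. Then reconcile that text with the two blinding statements in Section 10 and with its statement that no PHI is shared.

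The cost is coordinator time for about 15 image pairs and videos, plus protocol wording. Images already captured can be cropped, so no visit or procedure changes. Reviewers lose whole-face context for the GAIS, which matters little for an endpoint about submental tissue. Cropping reduces the cues but does not remove them: tan and facial hair on the neck and jawline stay partly visible.

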### 3. Study Design

This is a single-center, unblinded, non-randomized, non-controlled study designed to follow a total of up to 15 qualified and consenting subjects to receive one bipolar fractional radiofrequency microneedling treatment under an IRB approved protocol. The Principal Investigator(s) have been selected based on his expertise, qualifications (credentials, training, and medical specialty), subject access, previous clinical research, facilities, and interest in this particular field of research.

### 4. Study Population

Up to 15 subjects will be enrolled and treated at UT Southwestern in the Department of Plastic Surgery. Subjects will be identified from the clinical practice of [name], Department of Plastic Surgery.

Subjects who present for treatment with the Profound System will have the study explained to them, will be asked about their willingness to be involved in the study, and their willingness to sign an informed consent form. Included in this interview will be questioning from the investigator or staff member about any privacy concerns the individual may have.

Prior to any study procedures each Subject will read and sign an Informed Consent Form, explaining the purpose, design, risks and duration of the study. By signing the consent form, subjects indicate that they are willing to have their full-face photograph and acknowledge that these photos may be used for scientific publication. If the subjects decline permission to be photographed, they may not participate in the study since the photographic documentation of treatment outcome is an important measure of evaluation.

Subjects should abstain from undergoing any dermatological treatments during entire study duration.

## 5. Inclusion/Exclusion Criteria

### 5.1 Inclusion Criteria

- a. Healthy male and female adults between ages 21-70 years of age.
- b. Desire skin laxity lift of the submental region.
- c. Confirmed BMI  $\leq 35$ .
- d. Subjects who can read, understand, and sign the Informed Consent Form.
- e. Subjects willing and able to comply with all study requirements.
- f. Fitzpatrick skin type I-VI.
- g. Submental fat graded by the Investigator as  $\geq 1$  using the Clinician-Reported Submental Fat Rating Scale (CR-SMFRS, see Appendix D).
- h. Subject is willing not to undergo any type of aesthetic procedure that could confound the study device treatment effects until he/she completes the study.

### 5.2 Exclusion Criteria:

- a. Active localized or systemic infections, that may alter wound healing.
- b. Immunocompromised subjects.
- c. Subjects with coagulation disorder.
- d. History of skin photosensitivity disorders, or use of photosensitizing drugs (e.g., tetracycline or sulfa drugs).
- e. Pregnant and/or lactating (All female volunteers will be advised about using birth control during the period of study).
- f. Excessive skin laxity on the submental and neck (Submental Skin Laxity Grade: SMSLG 4, Appendix E), or other anatomical feature for which reduction in SMF which may, in the judgment of the investigator, result in an aesthetically unacceptable outcome.
- g. Scarring in areas to be treated.
- h. Tattoos in the treatment areas to be treated.
- i. Significant open facial wounds or lesions.
- j. Severe or cystic acne in treatment areas.
- k. Current active smoker.
- l. Use of Accutane (Isotretinoin) within the past 6 months.
- m. Use of topical retinoids within 48 hours.

- n. Use of prescription anticoagulants.
- o. Pacemaker or internal defibrillator.
- p. History of skin disorders resulting in abnormal wound healing (i.e. keloids, extreme dry and fragile skin).
- q. Subjects on current oral corticosteroid therapy or within the past 6 months
- r. Metal implants in the treatment area.
- s. In the opinion of the investigator, subject is unwilling or unable to adhere to all study requirements, including application and follow-up visits.
- t. Subjects with a history of radiation therapy to the treatment area.
- u. Subject has a history of allergy to lidocaine or ester-based local anesthetics.
- v. Subjects with significant cardiac history or rhythm disturbance who may be unable to tolerate lidocaine with epinephrine.
- w. Subjects with any skin pathology or condition in the treatment area that could interfere with evaluation or with the use of typical ancillary medical treatments or care used before, during or after treatments (e.g. psoriasis, rosacea, eczema, seborrheic dermatitis, vitiligo, hyper or hypo-skin pigmentation conditions such as post inflammatory hyperpigmentation).
- x. Subjects who are unwilling to shave excessive hair in the treatment area that might influence or impair evaluation in the opinion of the Investigator.
- y. Subjects have undergone skin resurfacing or tightening treatments in the treatment area over the past year.
- z. Subjects have undergone dermatological treatments such as fillers and neurotoxins for the past 6 months in the treatment area.
- aa. Subjects have undergone laser and light treatments in the treatment area over the past 3 months.
- bb. Subjects have undergone superficial peel or microdermabrasion within 4 weeks.

## 6. Study Endpoints

### 6.1 Primary Endpoints

#### 6.1.1 Primary Efficacy Endpoint

- Overall volume change of treated tissue in the submental region
  - Percent change from baseline of soft tissue surface area assessments that characterize the degree of stretch, compression, lift and volumization, as measured using the Markerless Tracking feature on Canfield's H2 3D Imaging System

### 6.1.2 Primary Safety Endpoint

- Incidence, severity, and relatedness of adverse events

## 6.2 Secondary Endpoints

- Improvement in overall lifting of treated tissue in the submental region via Blinded Evaluation of Baseline (pre-procedure) and Day 180 (post-procedure) photos and video obtained via the H2 3D Imaging System and Standup Vectra
- Blinded Reviewers assessment of improvement via the GAIS (Baseline vs. Day 180).
- Subject Assessment of Pain
  - The subjects' assessment of pain will be completed using an 11-point pain scale, where 0 = no pain, 10 = extreme pain (See Appendix A)
- Improvement in skin texture and laxity
  - Micro-biopsies for histology/gene expression
  - High-resolution ultrasound (HRUS)
  - Transepidermal Water Loss Measurements (TEWL)
  - Optical Coherence Tomography (OCT)
  - BTC 2000

Primary Endpoint Analysis:

### **Safety Endpoint**

Safety will be determined based on adverse event data collected from both the Profound treatment visit and all follow-up evaluations of the treated areas. The Primary Safety Endpoint will be the incidence rate, severity, and relatedness of the adverse events that are observed in the study. All adverse events that arise during the course of the study will be recorded and summarized in the final study report.

